7.3.2. Discontinuation of Study Therapy

Patients will be discontinued from the study treatment in the following circumstances:

- Enrollment in any other clinical trial involving a study drug or enrollment in any other type of medical research judged not to be scientifically or medically compatible with this study.
- The patient, for any reason, requires treatment with another therapeutic agent that has been demonstrated to be effective for treatment of the study indication; discontinuation from study therapy occurs prior to introduction of the new agent.
- Investigator/Physician Decision
 - The investigator/physician decides that the patient should be withdrawn from the study due to an intercurrent illness or change in the patient's condition that renders the patient unsuitable for further treatment in the opinion of the investigator.

- Any study therapy-related event that is deemed life-threatening, regardless of grade, warrants discontinuation of that therapy and/or discontinuation from all therapy if appropriate in the opinion of the investigator.
- If the patient has progressive disease (PD, confirmed by irRECIST or unconfirmed but with clinically worsening/deterioration [Section 10.1.5.1 and Table JFCQ.10.1]).
- Any event(s) which would require a given study therapy to be modified by more than 2 dose reductions or to be held for more than 6 weeks following Day 1 of the most recent cycle warrants discontinuation of that therapy.
- The patient becomes pregnant during treatment.
- Patient Decision
 - The patient or patient's designee (for example, parents or legal guardian) requests to be withdrawn from the study or study treatment.
- Sponsor Decision
 - The sponsor stops the study or stops the patient's participation in the study for medical, safety, regulatory, or other reasons consistent with applicable laws, regulations, and good clinical practices (GCP).
- The patient is significantly noncompliant with study procedures and/or treatment.
- An unacceptable AE/toxicity (for example, a persistent moderate toxicity that is intolerable to the patient).
- A Grade 3 to 4 IRR, and potentially other drug-related AEs, as specified in Section 9.4.1 below.

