- If a patient has confirmed radiographic progression (i.e., 2 scans at least 4 weeks apart demonstrating progressive disease) per irRECIST, but the patient is achieving a clinically meaningful benefit, and there is no further increase in the tumor burden at the confirmatory tumor imaging, an exception to continue treatment may be considered following consultation with the Sponsor.
- Any patient deemed clinically unstable should be discontinued from trial treatment at first radiologic evidence of PD and is not required to have repeat imaging for PD confirmation.
- In patients who discontinue study therapy without documented disease progression, every effort should be made to continue monitoring their disease status by tumor imaging using the same imaging schedule used while on treatment every 6 weeks (± 5 days), until (1) the start of new anti-cancer treatment, (2) disease progression, (3) death, or (4) the end of the study, whichever occurs first.

The following exploratory efficacy measures will be collected at the times shown in the Study Schedule ([Attachment 1](#)). Confirmation by 2 consecutive observations at least 4 weeks apart is required for CR, PR, and PD for both assessments to assign best response for each patient:

- immune-related CR (irCR): disappearance of all lesions
- immune-related PR (irPR): $\geq 30\%$ decrease of total tumor burden from baseline
- immune-related PD (irPD): $\geq 20\%$ increase of total tumor burden from the nadir
- immune-related SD (irSD): fail to meet criteria for irCR or irPR in the absence of irPD

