5.5.6.5. Exploratory Outcome and Methodology Based on irRECIST

The irORR, irDCR, irDOR, and irPFS assessment based on adapted RECIST 1.1 (irRECIST) will be used for exploratory analysis to account for the unique tumor response characteristics

seen with treatment of pembrolizumab. irRECIST will be applied as detailed in the study protocol, and the resulting data will be included in the clinical database.

Objective response rate (irORR) is defined as the proportion of evaluable patients achieving a best overall response of PR or CR per irRECIST. Particularly, the best overall response by irRECIST is closely related to confirmed response by RECIST. IrORR further captures responses after unconfirmed PD and it does not require confirmation. In addition, patients’ responses after start of new anticancer therapy are excluded from the determination of best response. For example:

- If the best response by RECIST is CR, then the best response by irRECIST is CR.
- If the best response by RECIST is PR, SD, or PD, the best response by irRECIST is the best response over the initial assessment (prior to PD by RECIST) and the confirmation stage.

Overall, the best response by irRECIST should be the same or better than the best response by RECIST criteria.

[figure not shown]
IrPFS: The date from the treatment started date to the time of PD assessed by irRECIST or death from any cause, whichever comes first.

- If the initial PD is confirmed, then the date of immune-related (ir)PD is the initial PD date by RECIST.
- If the initial PD is unconfirmed, then the date of irPD is the date of second non-consecutive PD.

Duration of response by irRECIST: The duration of response is defined from the date of first documented irCR or irPR (responder) to the date of irPD or the date of death due to any cause, whichever is earlier.

[figure not shown]
Graphic Example:

Scenario 1: The initial PD is confirmed at the next scan (consecutive PD). The efficacy variables by irRECIST and RECIST are the same.

Scenario 2: The initial PD is not confirmed at the next scan (non-consecutive PD). The efficacy variables by irRECIST and RECIST may be different.

PFS by irRECIST

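### After an unconfirmed first PD, the SAP dates irPD at a second isolated PD without asking for confirmation, which does not match the protocol's consecutive-scan rule (exploratory irPFS and irDOR only)

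*SAP*

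**What the plan says.** SAP 5.5.6.5 (exploratory analysis by irRECIST) gives two rules for the irPD date. For a confirmed first PD: "If the initial PD is confirmed, then the date of immune-related (ir)PD is the initial PD date by RECIST". For an unconfirmed one: "If the initial PD is unconfirmed, then the date of irPD is the date of second non-consecutive PD". The section's two scenarios show what confirmed means here. A PD seen again at the next scan is consecutive and confirmed. A PD not seen at the next scan is non-consecutive and unconfirmed. The irPD date ends irPFS, and it also ends irDOR: "The duration of response is defined from the date of first documented irCR or irPR (responder) to the date of irPD", or to death if earlier.

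The same section states that "irRECIST will be applied as detailed in the study protocol". Protocol 10.1.5.1, in the sentence that introduces its irCR, irPR, irPD and irSD definitions, reads: "Confirmation by 2 consecutive observations at least 4 weeks apart is required for CR, PR, and PD for both assessments to assign best response".

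Confirmed PD appears elsewhere in the protocol. Section 7.3.2 ties progression-based discontinuation to PD that is "confirmed by irRECIST or unconfirmed but with clinically worsening/deterioration". Section 10.1.3.1.2 and the treatment-period schedule in Attachment 1 continue imaging until progression is confirmed, with an exception in the schedule for patients who are clinically unsuitable to wait.

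**The concern.** The immune-related criteria are there so that one isolated PD scan in a patient on immunotherapy does not count as progression. The SAP gives that protection to the first PD and withdraws it from the second. It offers no reason for the difference, although it says it follows the protocol. In the SAP's own vocabulary, the second non-consecutive PD is a PD that did not confirm the first, and nothing requires it to be confirmed in turn.

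At stake are irPFS times, and irDOR times in irCR or irPR responders, for patients whose scans fluctuate. Such a patient can be given an event although no two consecutive scans show PD and study treatment may still be continuing. A time that would otherwise be censored becomes a shorter time with an event.

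**Working it through.** **Inputs.** Scans every 6 weeks (±5 days) from first dose (protocol 10.1.1, 10.1.3.1.2); 54 planned evaluable patients in Part B (protocol 12.1, SAP 5.1); the two SAP date rules and the protocol confirmation sentence set out above.

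**The plan's own figure.** The plan states no number for this rule. Its one design figure, 83% power for the ORR test, does not enter the point but does reproduce. With n = 54, the smallest r with P(X ≥ r | p = 0.20) ≤ 0.10 is r = 16. This gives an exact alpha of 0.0597 and power P(X ≥ 16 | p = 0.35) = 0.8338. With r = 15, alpha is 0.1068, which is too large.

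**Is the next scheduled scan late enough to confirm?** Six weeks is 42 days. With each scan free to move by 5 days, the shortest gap between two scheduled scans is 42 − 10 = 32 days, more than the 28 days required. Two consecutive scheduled scans therefore always meet the 4-week condition.

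**The rules compared.**

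- SAP rule: if the scan after the first PD is PD, irPD is the first PD date; otherwise irPD is the date of the second PD.
- Consecutive rule: irPD is the first PD that is followed by PD at the next scan; if there is none, the time is censored at the last scan.
- Proposed rule: as the consecutive rule, but a later PD with no subsequent scan counts on its own date.

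SAP 5.5.6.5 gives no separate censoring date for irPFS, so I assume the last scan, by analogy with RECIST PFS. The sequences are hypothetical, 6-weekly from week 6, with no deaths.

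| Scan sequence | SAP rule | Consecutive rule | Proposed rule |
|---|---|---|---|
| PD-SD-PD-SD-SD | event wk 18 | censored wk 30 | censored wk 30 |
| SD-PD-SD-PD-SD-SD | event wk 24 | censored wk 36 | censored wk 36 |
| SD-PD-SD-PD-SD-PD-PD | event wk 24 | event wk 36 | event wk 36 |
| PR-PR-PD-PR-PD-PR | event wk 30 | censored wk 36 | censored wk 36 |
| SD-PD-SD-PD-PD | event wk 24 | event wk 24 | event wk 24 |
| SD-PD-PD | event wk 12 | event wk 12 | event wk 12 |
| SD-PD-SD-PD (last scan) | event wk 24 | censored wk 24 | event wk 24 |

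In the first row the difference is 30 − 18 = 12 weeks, and an event replaces a censored time. RECIST 1.1 PFS for that patient is 6 weeks under any of these rules. In the responder row (fourth), irDOR from the first PR at week 6 is 30 − 6 = 24 weeks with an event under the SAP, against 36 − 6 = 30 weeks censored.

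The SAP and the consecutive rule agree whenever the first or the second PD is repeated at the next scan. They part only when a second PD is followed by a non-PD scan or by no scan.

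**How often.** The documents give no rate. If 2%, 5% or 10% of 54 patients showed two isolated PD scans (assumed rates), that would be 1.1, 2.7 or 5.4 patients, or roughly 1 to 5 irPFS times.

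**The case against.** The strongest reply is that the protocol has no irPFS or irDOR date rule to break. The two-consecutive requirement is stated for assigning best response. Protocol 12.2.7.1 names the immune-related endpoints and refers to the SAP for detail, and 12.2.1 lets the SAP clarify analyses. The repeat-scan step in 10.1.5.1 and Table JFCQ.10.1 is written for the initial PD, and no text covers a second PD after an unconfirmed first. Nor is confirmation absolute. Clinically unstable patients stop at the first radiologic PD without a repeat scan, and the post-discontinuation schedule in Attachment 1 lets imaging end at confirmed or unconfirmed progression. All of this stands. It makes the extension to event dates an inference and not an explicit requirement.

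A second reply is that a note in 10.1.5.1 describes confirmed progression as two PD scans at least 4 weeks apart, without saying consecutive, so weeks 6 and 18 might qualify. This does not rescue the SAP rule. If the later PD confirmed the first, the SAP's own rule for a confirmed first PD would date irPD at week 6, not week 18. The SAP instead treats the first PD as unconfirmed and lets the second stand alone.

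A third reply is that the graphic examples in SAP 5.5.6.5 are not visible in the available text and might clarify the rule. That remains possible; the written rule as it stands does not.

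A reader might go further and infer that these irPFS and irDOR events are false, or that a fixed share of the times is wrong. The documents support neither. The events are unconfirmed under the protocol's consecutive-scan rule; whether the patient had truly progressed is not known. When the second PD is the last scan, it may well be genuine.

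**Conclusion.** The point holds as a small mismatch between the SAP and the protocol principle it says it applies. After an unconfirmed first PD, the SAP accepts a second PD as irPD with no confirmation, so a patient with two isolated PD scans gets an irPFS event that the consecutive-scan rule would not give, or would give later. In the worked case the event falls at week 18 where the consecutive rule censors at week 30. irDOR is affected only in irCR or irPR responders.

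This rests on two assumptions: that the protocol's confirmation rule is meant to govern irPD dates as well as best response, which its use of confirmed PD for progression-based stopping and for ending on-treatment imaging supports; and that irPFS without irPD or death is censored at the last scan. The number of patients affected is unknown.

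It would be wrong to read this as touching every second PD, since nothing changes when the next scan confirms it. It would also be wrong to read it as touching the main results. irPFS and irDOR are exploratory (protocol 6.3, 12.2.7.1). Primary ORR, its alpha and power, and RECIST 1.1 PFS and DOR are unaffected.

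**What to change.** Replace the SAP rule for an unconfirmed first PD with one to this effect: if the initial PD is not confirmed, irPD is dated at the first later PD that is itself confirmed by the next consecutive assessment at least 4 weeks later. Use the same date for irDOR.

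Add, as an explicit analysis convention and not as a protocol rule, that a later PD with no subsequent tumor assessment counts as irPD on its own date. This keeps possibly genuine progression at the last scan from being censored. Neither change alters any treatment or imaging rule.

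If the sponsor does intend an unconfirmed second PD to count, the SAP should say so, record it as a departure from protocol 10.1.5.1, and show irPFS and irDOR under the confirmed-PD rule as a sensitivity analysis.

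The cost is a sentence or two in the SAP and minor programming, with no new data. The downside is a few more censored irPFS times.

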5.6. Analysis of Safety Data

5.6.1. Extent of Exposure

5.6.1.1. Necitumumab

- Number of cycles received by patient
- Number of patients treated by cycle
- Duration of treatment (in weeks) = $[(\text{Date of last dose} - \text{date of first dose}) + 14] \div 7$
- Cumulative dose (mg) = Sum of all doses administered
- Dose intensity (mg/week) = $(\text{Cumulative dose}) \div (\text{Duration of treatment})$
- Relative dose intensity (%) = $\text{Dose intensity (mg/week)} \div (600 \text{ or } 800 \text{ mg} * 2 / 3 \text{ weeks})$
- Number of dose reductions = Total number of reduction steps comparing the planned dose level before each infusion (as entered in the CRF) to the protocol planned dose level as referenced in the table in below.
- Dose delay as recorded on the CRF.

Table JFCQ.5.3. Dose Reductions for Necitumumab

Dose Level	Necitumumab
Starting Dose	800 mg
First Dose Reduction	600 mg
Second Dose Reduction	400 mg

Note: Actual dose levels entered in the CRF will be rounded to the nearest dose level listed in this table (e.g., any necitumumab dose level ≥ 700 mg will be rounded to 800 mg for the purpose of the dose reduction calculation; any necitumumab dose level < 400 mg will be rounded to 400 mg).

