9.4. Selection and Timing of Doses

The first treatment will be administered within 7 days of enrollment. Study treatment will be administered as described in Section 9.1.

A cycle is defined as an interval of 21 days.

Administration of pembrolizumab Day 1 dose, followed by necitumumab will trigger the start of a new cycle. Infusions administered within 3 days before or after the planned infusion time point due to holidays, weekends, bad weather, or other unforeseen circumstances will be permitted and not counted as a protocol deviation. The necitumumab Day 8 dose can be delayed up to 5 days. Beyond that, the Day 8 dose will have to be omitted in order to maintain the 21 day cycle. **A minimum of 7 days' interval between any necitumumab doses must be maintained.**

A patient may continue to receive study treatment until he or she meets 1 or more of the specified reasons for discontinuation (as described in Section 7.3), or complete remission is diagnosed (as described in Section 8.1).

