5.6.1.2. Pembrolizumab

- Number of cycles received by patient
- Number of patients treated by cycle
- Duration of treatment (in weeks) = $[(\text{Date of last dose} - \text{date of first dose}) + 21] \div 7$
- Cumulative dose (mg) = Sum of all doses administered
- Dose intensity (mg/week) = (Cumulative dose) \div (Duration of treatment)
- Relative dose intensity (%) = Dose intensity (mg/week) \div (200 mg / 3 weeks)
- Dose delay as recorded on the CRF.

The relative dose intensity will be additionally presented categorized (that is, number and percentage of patients with relative dose intensity of $< 60\%$, $\geq 60\%$ - $< 80\%$, $\geq 80\%$ - $< 90\%$, $\geq 90\%$ - $< 110\%$, $\geq 110\%$).

Moreover, the number and percentage of patients with any dose delay, with any dose reduction (reduction to first or second dose level) will be presented as well as the number (%) of patients with infusion interrupted.

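### The fixed 14-day tail in the SAP's necitumumab duration formula misstates relative dose intensity when a patient's last necitumumab dose is a Day 1 dose or a late Day 8 dose

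*SAP*

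**What the plan says.** Necitumumab is given on Days 1 and 8 (Protocol 9.1), and in Protocol 9.4 "A cycle is defined as an interval of 21 days". The same section covers departures from schedule. On lateness: "The necitumumab Day 8 dose can be delayed up to 5 days". On longer delays: "Beyond that, the Day 8 dose will have to be omitted in order to maintain the 21 day cycle". On spacing: "A minimum of 7 days' interval between any necitumumab doses must be maintained".

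SAP 5.6.1.1 derives exposure from "Duration of treatment (in weeks) = $[(\text{Date of last dose} - \text{date of first dose}) + 14] \div 7", with no condition on which day of the cycle the last dose fell. Dose intensity is cumulative dose over that duration. RDI divides dose intensity by a planned rate of two 600 mg or 800 mg doses per 3 weeks.

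For pembrolizumab, a Day 1 drug, SAP 5.6.1.2 uses the same construction but adds 21 days after the last dose. It also states: "The relative dose intensity will be additionally presented categorized". The bands are below 60%, 60 to below 80%, 80 to below 90%, 90 to below 110%, and 110% or more.

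**The concern.** The number 14 is 21 minus 7, so it assumes that the last dose was given exactly 7 days after Day 1 of the final cycle. The protocol permits other endings. When the last dose is a Day 1 dose, the final cycle is counted as 14 days although the planned rate still expects two doses in 21 days. The missing dose then shortens its own denominator. When the last dose is a late Day 8, the final cycle is counted as longer than 21 days.

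At stake are treatment duration, dose intensity, RDI and the RDI categories. Errors are largest in patients with few cycles, and these are the patients in whom an exposure table says most about tolerability.

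**Working it through.** Inputs: cycle of 21 days, with Day 8 up to 5 days late (Protocol 9.4); doses on Days 1 and 8 (Protocol 9.1); the 14-day tail and the planned rate of 2 doses per 3 weeks (SAP 5.6.1.1); the RDI bands (SAP 5.6.1.2). The dose cancels from RDI, so results are identical at 600 mg and 800 mg.

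**Where the formula works.** With n full on-time cycles, last minus first dose is 21(n−1)+7 days. Adding 14 gives 21n days, or 3n weeks. The 2n doses give RDI = (2n/3n) ÷ (2/3) = 100% for every n.

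**Last dose is a Day 1 dose, all earlier doses on time.** There are 2n−1 doses.
- SAP duration = [21(n−1)+14]/7 = 3n−1 weeks, so RDI = 1.5(2n−1)/(3n−1).
- Whole-cycle duration = 3n weeks, so RDI = (2n−1)/(2n).
- The ratio of the two is 3n/(3n−1), always above 1.

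Example at 800 mg, n=1: the SAP gives 800/2 = 400 mg/week against a planned 1600/3 = 533.3, or 75.0%. The whole cycle gives 800/3 = 266.7 mg/week, or 50.0%.

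| Cycles | SAP RDI | Whole-cycle RDI | Gap (points, from unrounded values) | Band, whole-cycle to SAP |
|---|---|---|---|---|
| 1 | 75.0% | 50.0% | 25.0 | <60 to 60–<80 |
| 2 | 90.0% | 75.0% | 15.0 | 60–<80 to 90–<110 |
| 3 | 93.8% | 83.3% | 10.4 | 80–<90 to 90–<110 |
| 4 | 95.5% | 87.5% | 8.0 | 80–<90 to 90–<110 |
| 5 | 96.4% | 90.0% | 6.4 | no change |
| 8 | 97.8% | 93.8% | 4.1 | no change |
| 12 | 98.6% | 95.8% | 2.7 | no change |

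An earlier cycle delay does not remove the error. With n=4 and one 7-day delay, the SAP duration is 63+7+14 = 84 days (12 weeks) and RDI is 5600/12 ÷ 533.3 = 87.5%. Over whole cycles it is 91 days (13 weeks) and 80.8%.

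**Final Day 8 given d days late.** SAP duration is 21n+d days, so RDI = 21n/(21n+d) where all 2n doses were given. For n=1 this runs from 21/22 = 95.5% (d=1) to 21/26 = 80.8% (d=5), against 100%. For n=2, d=5 it is 42/47 = 89.4%. The two values at d=5 fall one band too low.

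**Day 8 omitted only in an earlier cycle.** With the final Day 8 on time, n=4 gives 7 doses over 12 weeks, which is 87.5% by either method, so there is no error. The same seven doses score 87.5% if an early Day 8 was missed and 95.5% if the last one was.

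**The case against.** The strongest objection is that a whole final cycle is a convention. The SAP has no explicit rule that a started cycle counts as 21 days, and a patient who stops for good after Day 1 had no further dose due. That is fair as far as it goes. But the planned rate is set per 3 weeks, and the same SAP credits a pembrolizumab dose on the same Day 1 with 21 days. The split between 87.5% and 95.5% for identical doses over four cycles is not a convention that anyone would choose. Counting only to the next planned dose (7 days after a Day 1 dose) would give 150% for a single dose, so it is no alternative.

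Several limits stand. The omission rule in Protocol 9.4 exists to keep later cycles on schedule, so most omissions under it need not be final. Cumulative dose and number of cycles are reported separately and are unaffected. Protocol 12.2.5 and 12.2.10 also plan summaries of dose omissions, which keep a skipped Day 8 visible, although SAP 5.6.1 does not list omissions.

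A reader might infer three stronger things that the documents do not support:
- That RDI is overstated whenever a Day 8 is omitted. It is overstated only when the patient's very last necitumumab dose is a Day 1 dose.
- That the Part B feasibility objective is compromised. Protocol 6.2 lists safety events, DCR, DOR, PFS, OS, PK and immunogenicity as its means and does not name dose intensity.
- That DLT calls are affected, because the 1-cycle value of 75.0% coincides with the 75% in Protocol 9.4.1.1. That criterion rests on planned dose in the first cycle and does not use the SAP's RDI.

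**Conclusion.** The formula as written gives a wrong duration, and hence a wrong dose intensity and RDI, for two kinds of final dose. After a final Day 1 dose, RDI is overstated by 25.0 points at 1 cycle, falling to 8.0 at 4 cycles and 4.1 at 8. The band is too high for 1 to 4 cycles and unchanged from 5. After a late final Day 8, RDI is understated, by up to 19.2 points (100 − 80.8) at 1 cycle. The two errors fall on different patients and cannot be relied on to cancel.

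This rests on two assumptions. The first is that a started cycle counts as 21 days, for the reasons above. The second is that the RDI bands apply to necitumumab although they are printed under the pembrolizumab heading. The paragraph that follows them speaks of first and second dose levels, which the SAP defines only for necitumumab (Table JFCQ.5.3). If the bands were for pembrolizumab alone, the band shifts would fall away but the RDI errors would remain.

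The documents give no frequency for either ending, so the effect on the trial-level summary cannot be sized. It is confined to descriptive exposure summaries. Cumulative dose, DLT counts, ORR and its test, and the named feasibility endpoints are untouched.

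**What to change.** In SAP 5.6.1.1, define necitumumab duration in weeks as [(Day 1 date of the last cycle in which necitumumab was given − date of first dose) + 21] ÷ 7. Take Day 1 from the recorded cycle visit. Protocol 9.4 starts a cycle with the pembrolizumab dose followed by necitumumab, while Protocol 9.4.1.2.2.1 says necitumumab should not be delayed for pembrolizumab toxicity, so Day 1 needs a definition that survives a held pembrolizumab dose.

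This agrees with what the pembrolizumab formula achieves, since last dose plus 21 days reaches the cycle end for a drug given on Day 1. It leaves patients with an on-time final Day 8 unchanged and corrects both errors. While editing, state that the RDI bands apply to both drugs, if that is intended.

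The cost is one line of SAP text and one line of derivation code. Some RDI values will fall and some will rise. No dosing rule is touched.

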9.4.1.2.2. Necitumumab

Prior to each administration of necitumumab, all toxicities associated with necitumumab must have resolved to Grade ≤ 2 (except for alopecia and skin toxicity) or baseline. Pretreatment laboratory data may not be older than 72 hours (Day 1 of each cycle) or 24 hours (Day 8 of each cycle).

If the criteria are not met at the time of a planned treatment, the following general rules for the management of treatment delays apply:

- In the case of reversible Grade 3-4 necitumumab-related toxicity (for example, fatigue, anorexia, and fever), administration of necitumumab will be at the reduced dose (refer to [Section 9.4.1.2.2.1](#)) or interrupted, but pembrolizumab will continue according to the planned schedule.
- If administration of necitumumab is delayed for more than 6 weeks (2 cycles) after Day 1 of the most recent treatment cycle, the patient should be discontinued from necitumumab treatment.

9.4.1.2.2.1. Necitumumab Dose Modifications

The following are general dose-modification guidelines for toxicity associated with necitumumab. Please see [Section 9.4.1.3](#) for specific information on the management of necitumumab-related hypersensitivity/IRRs, skin reactions, conjunctivitis, and hypomagnesemia.

For patients starting Cycle 1 in Part A and possible Part B of the study at necitumumab 600 mg on Days 1 and 8, one dose reduction is permitted. Patients who cannot tolerate necitumumab 400 mg should discontinue necitumumab; such patients may continue with pembrolizumab as a single agent.

For patients starting Cycle 1 at dose level 800 mg on Days 1 and 8 in Part A and possible Part B and Part C of the study, 2 dose reductions are allowed following reversible CTCAE Grade ≥ 3 AEs that require delay of necitumumab treatment for up to 6 weeks following Day 1 of the most recent treatment cycle, unless DLT criteria are met (Cycle 1 Parts A and C). In this setting, necitumumab may be re-administered at a reduced dose (600 mg) if necessary only if AE is resolved to Grade ≤ 2 . A second dose reduction is permitted for this level of event (Grade ≥ 3). Necitumumab must be discontinued if further dose reduction is required beyond 400 mg on Days 1 and 8 Q3W. The patient may continue to receive pembrolizumab as a single agent.

Necitumumab dose adjustments are allowed both within a cycle and between cycles.

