5.4. Patient Disposition

A detailed description of patient disposition will be provided. It will include a summary of the number and percentage of patients never treated, still under treatment (that is, have not completed the End of Treatment [EOT] visit) at data cut-off date will be summarized. Patients discontinued from treatment will be presented by reason.

The number and percentage of patients with any important protocol violation will be summarized overall and by type of violation. The pre-defined important protocol violations are listed in below; in addition, any other protocol violations reviewed by CRP and deemed to be important protocol violations will be included in the summary.

- Patient failed to meet study inclusion/exclusion criteria
- Study treatment continued after progressive disease (PD) occurred
- Patient received concurrent prohibited therapy (Listing to identify Anatomical Therapeutic Chemical (ATC) codes is to be provided for medical review) while receiving study treatment.
- Necitumumab continued after Grade 3-4 infusion reaction occurred (as defined by dictionary term “Infusion related reaction”)
- Post-baseline tumor assessments use different methods than baseline assessment
- Actual doses of study drug was more than 10% greater than protocol defined dose (800 mg for necitumumab, 200mg for Pembrolizumab), at any of dose administration
- Patient started next cycle less than 18 days later after Day 1 of the most recent treatment cycle
- Patient received more than 2 dose reductions of necitumumab

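### The SAP measures necitumumab dose reductions and overdoses against 800 mg for every patient, so correctly dosed 600 mg patients in Cohort 1 are scored as reduced and an 800 mg dose given to one of them is not flagged

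*SAP*

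**What the plan says.** **Counting reductions.** SAP 5.6.1.1 compares the planned dose level before each infusion, as entered on the CRF, "to the protocol planned dose level as referenced in the table in below". That table (JFCQ.5.3) has one ladder: 800 mg is the starting dose, 600 mg the first reduction and 400 mg the second. Recorded levels are rounded to the nearest rung. A level of 700 mg or more "will be rounded to 800 mg for the purpose of the dose reduction calculation", and at the lower end "any necitumumab dose level < 400 mg will be rounded to 400 mg". The end of SAP 5.6.1.2 treats reaching the first or second reduced level as having had a reduction.

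**Violations.** SAP 5.4 predefines two relevant important violations: "Actual doses of study drug was more than 10% greater than protocol defined dose", with the reference given as "800 mg for necitumumab, 200mg for Pembrolizumab"; and "Patient received more than 2 dose reductions of necitumumab".

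**Protocol.** Section 8.1 assigns Cohort 1 to 600 mg on Days 1 and 8, keeps patients at their cohort's level and rules out escalation within a cohort. Section 9.4.1.2.2.1 says that for a 600 mg start "one dose reduction is permitted"; for an 800 mg start it allows two. The same section lets a reduced dose be raised again after at least two reduced administrations and consultation with the sponsor's physician.

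**Relative dose intensity.** In the same bullet list of SAP 5.6.1.1, the denominator is 600 or 800 mg, so there the 600 mg start is recognised.

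**The concern.** A reduction should mean that a patient's dose was lowered from what that patient was assigned. With 800 mg as the only reference, assignment to Cohort 1 is itself recorded as a reduction. SAP 5.2 summarises Part A by assigned dose level, so the error would fill the Cohort 1 column of a table used to describe tolerability at 600 mg, which is part of the Part A question.

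The overdose rule has the opposite fault. For anyone whose planned dose is below 800 mg the threshold is too high, and the predefined check misses doses well above plan.

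The 400 mg floor adds a third problem: a dose below the lowest listed level looks the same as 400 mg in the reduction count. Whether that also disables the violation on the number of reductions depends on how steps are counted, which the SAP does not state.

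**Working it through.** **Inputs.** Ladder 800/600/400 mg with its rounding rules (SAP 5.6.1.1); overdose margin 10% and reference 800 mg (SAP 5.4); Cohort 1 dose 600 mg (Protocol 8.1); Cohort 1 size 3 to 6 out of about 78 patients in all (SAP 5.1).

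**1. Rounding rule reproduced.** The midpoint of the top two rungs is (600 + 800)/2 = 700 mg, which matches the SAP's cut. Every level below 400 mg maps to 400 mg.

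**2. Reduction count.** Steps = (reference − rounded level)/200, taking the deepest level reached.

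| Dose history | Reference 800 mg (SAP) | Reference = assigned start |
|---|---|---|
| 600 throughout | (800 − 600)/200 = 1 | (600 − 600)/200 = 0 |
| 600, then 400 | (800 − 400)/200 = 2 | (600 − 400)/200 = 1 |
| 800 throughout | 0 | 0 |

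All 3 to 6 Cohort 1 patients are therefore scored as reduced: 3/78 = 4% to 6/78 = 8% of the planned total, but 100% of their own column.

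**3. Inconsistency within the section.** Take a Cohort 1 patient with one full cycle, 600 mg on Days 1 and 8. Duration is (7 + 14)/7 = 3 weeks and dose intensity is 1,200/3 = 400 mg/week. Relative dose intensity is 400/(600 × 2/3) = 100%. The same patient is at full intensity by one rule and reduced by the other.

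**4. Overdose threshold.** Flag if dose > 1.10 × reference.
- SAP: 1.10 × 800 = 880 mg for everyone. Against a 600 mg plan: 1.10 × 600 = 660 mg.
- 800 mg given to a 600 mg patient: 800/600 − 1 = +33%, not flagged.
- Largest unflagged dose in that patient: 880/600 − 1 = +47%.
- An unplanned 800 mg dose in an 800 mg starter currently reduced to 600 mg (+33%) or 400 mg (800/400 − 1 = +100%) is also not flagged. If the 800 mg is a permitted re-escalation, it is not an overdose.

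**5. Can the count exceed 2?** The SAP asks for a total number of steps without defining a step. Three readings give different answers:
- *Depth below 800 mg after rounding.* Possible values are 0, 1 and 2. A history of 800, 600, 400, 200 gives 2 because 200 rounds to 400. A count above 2 is unreachable.
- *Sequential reductions, allowing re-escalation.* A history of 800, 600, 800, 600, 400 gives 1 + 1 + 1 = 3. A count above 2 is reachable.
- *Steps summed over infusions.* An unreduced 600 mg patient with 6 infusions gives 6 × 1 = 6.

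Under the first two readings, moving from 400 mg to anything lower adds no step. Under the third, an infusion below 400 mg scores the same as one at 400 mg.

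**The case against.** **The ladder follows the protocol.** Table JFCQ.5.3 has the same rungs as Protocol Table JFCQ.9.3, where 800 mg is level 0. That explains its origin, but a list of permitted levels is not a statement of where each patient started, and Cohort 1 starts one rung down.

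**Other safeguards exist.** The SAP 5.4 list is open: the sponsor's physician can add violations on review. Cumulative dose sums what was actually given, so low or high doses still enter relative dose intensity. A reader might infer that such doses are invisible. The documents do not support that; the accurate statement is that the predefined rules do not catch them.

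**The scope is small.** A Cohort 1 column showing every patient reduced would be noticed, and none of these rules enters the DLT assessment or the ORR test. This stands. A reader might also extend the miscount to all of Parts B and C, which would follow only if 600 mg were the recommended dose. SAP 5.11 pools Cohort 2 with Part B, which points to 800 mg.

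**The limit of two has protocol support.** Protocol 7.3.2 and 9.4.1.2.2.1 both tie discontinuation to more than two reductions. A reader might conclude that the SAP limit is simply wrong for 600 mg starters. The protocol itself carries both statements, so the texts need reconciling, and this review does not choose between them.

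**Conclusion.** The point holds for the reference dose. On the literal text, all 3 to 6 Cohort 1 patients are counted as having a reduction that did not happen, a true single reduction among them counts as two, and the predefined overdose rule misses doses 33% to 47% above plan (800 to 880 mg in a 600 mg patient). It also misses an unplanned return to 800 mg in a currently reduced patient. Levels below 400 mg are merged with 400 mg in the count.

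It is tempting to add that the violation of more than two reductions can never be triggered. That is true only if steps mean depth below 800 mg after rounding. With sequential counting and the re-escalation that the protocol permits, three is reachable, and SAP 5.4 does not say that it uses the rounded count. What the documents support is that the counting method is undefined and that a reduction below 400 mg adds nothing to it.

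The conclusion assumes that the table and the parenthesis in SAP 5.4 are programmed as written. A programmer who substituted 600 mg for Cohort 1 would avoid the error in the reference dose, but the SAP does not direct this. The consequence is limited to exposure and protocol-violation tables, mainly for Cohort 1.

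**What to change.** In SAP 5.6.1.1:
- Count reductions from each patient's assigned starting dose (600 or 800 mg), in line with the relative dose intensity formula.
- Report levels below 400 mg as recorded instead of rounding them up.
- Define a reduction step, including how a second reduction after re-escalation is counted.

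In SAP 5.4:
- Test overdose as more than 10% above the dose level planned for that patient at that infusion. A permitted re-escalation then changes the planned level and is not flagged.
- State whether the violation on the number of reductions uses the count from SAP 5.6.1.1.

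Reconcile SAP 5.4, Protocol 7.3.2 and the limits in Protocol 9.4.1.2.2.1 on how many reductions apply to a 600 mg start.

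The cost is SAP wording and small programming changes. The planned level before each infusion is already on the CRF, so no new data are needed.
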